## 7.2 Investigations

In case of coinciding investigations, the time point for blood collection for PK evaluation takes priority over any other scheduled study activities, e.g. blood pressure and local safety ECG. Where other activities are scheduled together with the PK blood collection, these will be performed in a sequence allowing for blood sampling exactly at the scheduled time point. The exact time of each activity will be recorded in the eCRF.

### 7.2.1 Sample collection for PK evaluation and samples preparation

The laboratory analysis will be carried out following the GCP and the applicable principles of Good Laboratory Practice (GLP) regulations of the Organisation for Economic Co-operation and Development (OECD).

The analytical procedures will be described in a separate analytical protocol. Validation data and details of the analytical procedures will be gathered in an analytical report that will be included in the clinical study report.

The breakdown of blood samples collection is reported in [Appendix 3](#).

#### 7.2.1.1 Determination of CHF6001 and related analytes in human plasma

Blood samples for the determination of plasma total [C], [C]-CHF6001, metabolite profiling (if required) and non-radiolabeled CHF6001, will be collected and processed according to an established laboratory manual at pre-dose and in the 0-240h interval after dosing, as follows:

- 22 blood samples of 4 mL for plasma non-radiolabeled CHF6001 will be collected at pre-dose (within 60 min from inhaled dosing) and at the following timepoints post inhaled dose: 15, 30, 60, 90 min, 2, 3.75, 5.75, 7.75, 9.75, 11.75, 13.75, 25.75, 49.75, 73.75, 97.75, 121.75, 145.75, 169.75, 193.75, 217.75 and 241.75 hours;
- 25 blood samples of 5 mL for plasma total [C] and [C]-CHF6001 will be collected at pre-dose (within 60 min from inhaled dosing) and at the following timepoints relative to the start of the IV infusion: 5, 10, 15 [end of infusion], 20, 25, 30, 45, 60 min, 2, 4, 6, 8, 10, 12, 24, 48, 72, 96, 120, 144, 168, 192, 216 and 240 hours;
- 25 blood samples of 10 mL for plasma [C] of the relevant metabolites will be collected at pre-dose (within 60 min from inhaled dosing) and at the following timepoints relative to the start of the IV infusion: 5, 10, 15 [end of infusion], 20, 25, 30, 45, 60 min, 2, 4, 6, 8, 10, 12, 24, 48, 72, 96, 120, 144, 168, 192, 216 and 240 hours;
- 2 blood samples of 2 mL for whole blood total [C] and [C]-CHF6001 will be collected at pre-dose (within 60 min from inhaled dosing) and 20 min after the start of infusion (for a total of 4 samples).

The processing, storage and shipment of samples are detailed in the laboratory manual document.

Day	Clock time (exemplary)	Time after inhaled administration	Time after start of i.v. administration	Time deviation allowed	PK timepoint inhaled administration	PK timepoint i.v. administration
1	08:00	Pre-dose		Within 60 minutes from inhalation	X 	X 

Clinical Study Code: CLI-06001AA1-02	Version No.: 1.0
EUDRACT No.: 2020-004201-31	Date: 19 October 2020

	09:00	Start of inhaled administration			
	09:15	15 min	± 2 min	X 	
	09:30	30 min	± 2 min	X 	
	10:00	60 min	± 5 min	X 	
	10:30	90 min	± 5 min	X 	
	10:45		Start of infusion (SOI)		
	10:50		SOI + 5 min	± 2 min	X 
	10:55		SOI + 10 min	± 2 min	X 
	11:00	2 h	SOI + 15 min (end of infusion)	± 2 min	X 
	11:05		SOI + 20 min	± 2 min	X
	11:10		SOI + 25 min	± 2 min	X
	11:15		SOI + 30 min	± 2 min	X
	11:30		SOI + 45 min	± 5 min	X
	11:45		SOI + 60 min	± 5 min	X
	12:45	3.75 h	SOI + 2 h	± 5 min	X
	14:45	5.75 h	SOI + 4 h	± 10 min	X
	16:45	7.75 h	SOI + 6 h	± 10 min	X
	18:45	9.75 h	SOI + 8 h	± 10 min	X
	20:45	11.75 h	SOI + 10 h	± 20 min	X
	22:45	13.75 h	SOI + 12 h	± 20 min	X
2	10:45	25.75 h	SOI + 24 h	± 20 min	X
3	10:45	49.75 h	SOI + 48 h	± 1 h	X
4	10:45	73.75 h	SOI + 72 h	± 1 h	X
5	10:45	97.75 h	SOI + 96 h	± 1 h	X
6	10:45	121.75 h	SOI + 120 h	± 1 h	X
7	10:45	145.75 h	SOI + 144 h	± 1 h	X
8	10:45	169.75 h	SOI + 168 h	± 1 h	X
9	10:45	193.75 h	SOI + 192 h	± 1 h	X
10	10:45	217.75 h	SOI + 216 h	± 1 h	X
11	10:45	241.75 h	SOI + 240 h	± 1 h	X

SOI: Start Of Infusion

: Fasted condition

Longer time deviations will be evaluated on a case by case basis during the Data Review Meeting.

**Metabolite profiling:** pooling across timepoints for each subject will be done. This will be followed

Clinical Study Code: CLI-06001AA1-02	Version No.: 1.0
EUDRACT No.: 2020-004201-31	Date: 19 October 2020

by chromatography (LC+AMS) and radio-peaks will be detected and quantified. For metabolites in plasma accounting for  $\geq 10\%$  of total radioactivity recovered in this matrix structural characterization may be performed, where possible.

#### ***7.2.1.2 Determination of CHF6001 and related analytes in human urine***

Urine samples for total [ $^{14}\text{C}$ ], metabolite profiling (if required) and [ $^{14}\text{C}$ ]-CHF6001 assessment will be collected at pre-dose from -12 hours to immediately before study drug inhaled administration (-12-0h) and at the following time frames relative to the start of the IV from pre-dose infusion: 0-4h, 4-8h, 8-12h, 12-24h, 24-48h, 48-72h, 72-96h, 96-120h, 120-144h, 144-168h, 168-192h, 192-216h and 216-240h, for a total of 14 urine collection intervals.

Subjects will be asked to empty the bladder before both dosing and before the end of each collection interval. All urine voided during the collection intervals will be retained. Access to the toilet will be controlled by the site staff.

Collection and processing are described in the laboratory manual document.

The following time deviations from theoretical post-dose times related to the end of the collection interval will be allowed:

For 4 and 8 hours post-dose	$\pm 10$ min
For 12 and 24 hours post-dose	$\pm 20$ min
For $>24$ hours post-dose	$\pm 30$ min

Longer time deviations will be evaluated on a case by case basis during the Data Review meeting.

**Metabolite profiling:** pooling across timepoints and subjects will be done. This will be followed by chromatography (LC+AMS) and radio-peaks will be detected and quantified. For metabolites in urine and feces (total excreta) accounting for  $\geq 10\%$  of total administered radioactivity structural characterization may be performed, where possible.

#### ***7.2.1.3 Determination of CHF6001 and related analytes in human feces***

Fecal samples for total [ $^{14}\text{C}$ ], metabolite profiling (if required) and [ $^{14}\text{C}$ ]-CHF6001 assessment will be collected at pre-dose from check-in (Day -1) to immediately before study drug inhaled administration (check-in -0h) and at the following time frames relative to the start of the IV infusion: 0-24h, 24-48h, 48-72h, 72-96h, 96-120h, 120-144h, 144-168h, 168-192h, 192-216h and 216-240h, for a total of 11 fecal collection intervals.

The feces samples will be pooled across the defined time windows. The time of each void will be recorded and then assigned to the appropriate collection interval. Collection and processing are described in the laboratory manual document.

**Metabolite profiling:** pooling across timepoints and subjects will be done. This will be followed by chromatography (LC+AMS) and radio-peaks will be detected and quantified. For metabolites in urine and feces (total excreta) accounting for  $\geq 10\%$  of total administered radioactivity structural characterization may be performed, where possible.

Clinical Study Code: CLI-06001AA1-02	Version No.: 1.0
EUDRACT No.: 2020-004201-31	Date: 19 October 2020

### 7.2.2 Blood collection for safety evaluation

The following blood samples will be collected at Screening and at discharge:

- **3.5 mL** of blood sample for serum **clinical chemistry testing** (creatinine, urea, aspartate aminotransferase (AST), alanine aminotransferase (ALT), Gamma-glutamyl transpeptidase ( $\gamma$ -GT), total bilirubin, alkaline phosphatase, sodium (Na), potassium (K)) and **fasting glucose**.
- **3.5 mL** of blood sample for serum **serology testing** (HIV1, HIV2, Hepatitis B and Hepatitis C) will be collected only at Screening.
- **4 mL** of blood sample for **haematology testing** (red blood cells count (RBC), white blood cells count (WBC) and differential (neutrophils, eosinophils, lymphocytes, monocytes) (% and values), total haemoglobin (Hb), haematocrit (Hct), platelets count (PLT)).

Below indications will be followed for safety evaluation in blood at screening:

- As for Exclusion criteria no. 3, in case clinically relevant abnormal laboratory values are observed, suggesting a temporary condition and requiring further clinical investigation, subject will be asked to return to clinic once before treatment, to perform again the testing measurement. If at that time no abnormalities are observed, subject can be included in the study, otherwise subject will be discharged and recorded as Screening Failure.

Blood collection and sample preparation will be performed according to procedures provided by the local laboratory which will be in charge to transmit the results and the laboratory normal ranges for entry in the eCRF.

### 7.2.3 Urine collection for safety evaluation

The following urine sample will be collected at Screening:

- urine sample for **urinalysis – quantitative** (proteins) and **urinalysis – qualitative** (ketones, microscopic examination of the sediment)
- urine sample for **drug test** (cannabinoids, opiates, cocaine, benzodiazepines, amphetamines, barbiturates)
- urine sample for **cotinine test**

The following urine samples will be collected on Day-1 of the Treatment Period:

- urine sample for **drug test** (cannabinoids, opiates, cocaine, benzodiazepines, amphetamines, barbiturates)
- urine sample for **cotinine test**

Urine collection and sample preparation will be performed according to procedures provided by the local laboratory which will be in charge to transmit the results to the Investigator for entry in the eCRF.

### 7.2.4 Blood Pressure

At Screening and on Day 1 of the treatment period (before blood sampling) Systolic and Diastolic Blood Pressure (SBP, DBP) will be measured in triplicate, within 5 minutes, at the following time points: **pre-dose and at 2,5 hours** after inhaled administration, for safety reasons. Subjects should

Clinical Study Code: CLI-06001AA1-02	Version No.: 1.0
EUDRACT No.: 2020-004201-31	Date: 19 October 2020

be resting in a quiet supervised setting with minimal stimulation (e.g. no television, loud music, computer games) and lay in a supine position for 5 minutes (whenever possible) before each measurement. No time deviations will be recorded for BP. Below indications will be followed for Blood Pressure measurement at Screening:

- As for Inclusion criterion no. 7, in case the values are out of the defined ranges (average of the triplicate parameters out of normal range i.e. Diastolic Blood Pressure 40-90 mmHg, Systolic Blood Pressure 90-140 mmHg), subject will repeat the Blood Pressure measurement. If the repeated values (the average of the triplicate parameters) are within the allowed ranges, subject can be included in the study, otherwise subject will be discharged and recorded as Screening Failure.

The single values and the average of triplicate Blood Pressure measurements will be reported in eCRF, and the average will be used to assess the inclusion criterion at screening.

### 7.2.5 Local Safety 12-Lead ECG

A local triplicate 12-lead digitalized Electrocardiogram (12-lead ECG) recording will be done and considered for safety purpose at Screening (before Blood pressure and blood sampling) to check the subject eligibility (according to exclusion criterion) and a local single 12-lead ECG will be performed on Day 1 of the study period at **predose and at 2,5 hours** after inhaled administration. No time deviations will be recorded for ECG.

Subjects should be resting in a quiet supervised setting with minimal stimulation (e.g. no television, loud music, computer games) and lay in a supine position for 5 minutes (whenever possible) before each measurement.

Below indications will be followed for Local ECG measurement at Screening:

- As for Inclusion Criterion no. 8, in case abnormalities are observed with Local ECG ( $40 \leq$  Heart rate  $\leq 110$  bpm,  $120$  ms  $\leq$  PR  $\leq 210$  ms, QRS  $\leq 120$  ms, QTcF  $\leq 450$  ms for males) subject will perform again the ECG measurement. If at that time the average of the triplicate ECG parameters is within the allowed ranges, subject can be included in the study, otherwise subject will be discharged and recorded as Screening Failure.

Below indications will be followed for local ECG measurement during the treatment period:

- A single 12-lead ECG measurement will be performed on Day 1, at predose and at 2 hours post dose (in resting conditions as much as possible)

The values of all ECG parameters and the overall ECG evaluation will be reported in eCRF, at Screening and the average will be used to assess the inclusion criterion.

### 7.2.6 Lung function evaluation

The lung function measurements will be assessed locally at Screening.

Spirometry will be done according to the recommendation of the Official Statement of the European Respiratory Society and American Thoracic Society [17], [18]. Lung function measurements will be done with subjects either standing or sitting with the nose clipped after at least 10 minutes rest. Values will be corrected for BTPS conditions.

Clinical Study Code: CLI-06001AA1-02	Version No.: 1.0
EUDRACT No.: 2020-004201-31	Date: 19 October 2020

The following parameters will be recorded:

- Forced Expiratory Volume in the 1st second (FEV1, L)
- Forced Vital Capacity (FVC, L)
- FEV1 % of predicted normal value
- FVC % of predicted normal value
- FEV1/FVC ratio

Predicted values of FEV1 will be calculated according to formulas reported by Quanjer et al [19].

For FEV1 and FVC, **the highest value from three technically satisfactory attempts** will be recorded in the eCRF (irrespective of the curve they come from). The chosen value should not exceed the next one by more than 150 mL. If the difference is larger, up to 8 measurements will be made and the largest value be reported. In order to be considered as technically satisfactory attempts, measurements should be free from cough and false-start. FEV1/FVC should be taken from the highest FEV1 and FVC values (even if not coming from the same curve).

Below indications will be followed for lung function measurement at screening:

- As for Inclusion Criterion no. 9, in case the criterion is not met, subject will repeat the test. If at that time the FEV1/FVC >0.70 and FEV1 >80% predicted, subject can be included in the study, otherwise subject will be discharged and recorded as Screening Failure.

The FEV1/FVC values will be provided as ratio. For eligibility purposes, values will be considered as acceptable if FEV1/FVC >0.70.

## 8. PHARMACOKINETIC ASSESSMENTS

Main objective of this study is to assess the absolute bioavailability, the mass balance and routes of elimination of CHF6001, using [C]-radiolabelled drug substance administered as an intravenous (IV) infusion concomitantly to an inhaled non-radiolabelled dose, in healthy volunteers.

Therefore, the following variables will be derived:

Following intravenous (IV) administration:

- Plasma [C]-CHF6001, AUC0-t iv, Cmax\_iv, tmax\_iv, AUC0-∞ iv, t1/2 iv, Vz, Vdss and systemic clearance (CL)
- Plasma [C]-total AUC0-t iv, Cmax\_iv, tmax\_iv, AUC0-∞ iv, t1/2 iv
- Urine and feces [C]-CHF6001 and [C]-total excreted fraction (Feu, Fef and Feu+f)
- Systemic blood clearance (CLblood) [C]-CHF6001
- Renal plasma and blood clearance (CLR and CLR\_blood) [C]-CHF6001
- Fraction of the relevant metabolites in plasma, and fraction of the relevant metabolites recovered in urine and feces (Frplasma, Frurine, Frfeces, Frurine+feces)
- Metabolized fraction (Femet)
- Blood to plasma ratio (Rb/p) [C]-CHF6001
- Blood to plasma ratio (Rbt/pt) [C]-total
- Hepatic extraction (Eh\_blood) [C]-CHF6001

Following inhaled administration:

Clinical Study Code: CLI-06001AA1-02	Version No.: 1.0
EUDRACT No.: 2020-004201-31	Date: 19 October 2020

- Plasma CHF6001  $AUC_{(0-t)}_{inh}$ ,  $C_{max\_inh}$ ,  $t_{max\_inh}$ ,  $AUC_{(0-\infty)}_{inh}$ ,  $t_{1/2\_inh}$ , absolute inhaled bioavailability ( $F_{inh}$ )

The pharmacokinetic analysis will be performed using WinNonlin Phoenix 6.2 or later (Pharsight Corporation, Palo Alto, CA, USA). Actual elapsed time from dosing will be used to estimate all individual PK parameters. Standard non-compartmental methods will be used for the calculation of the following parameters from the individual plasma drug concentrations versus time profile.

The following PK parameters will be calculated, whenever possible, for each subject based on the whole blood concentrations of [C]-CHF6001, plasma concentrations of CHF6001, plasma [C]-CHF6001 and plasma [C]-total radioactivity:

- $AUC_{0-t}$ : the area under the concentration-time curve from 0 to the last quantifiable concentration will be computed using the linear trapezoidal rule with linear interpolation;
- $AUC_{0-\infty}$ : the area under the concentration-time curve extrapolated to infinity will be calculated as the sum of  $AUC_{0-t}$  and a residual part extrapolated to infinite time. The residual area from the last concentration data point to infinite time is calculated using the approximation:

$$\int_t^{\infty} C_t dt = C_t / \lambda z$$

Where  $\lambda z$  is the first order terminal rate constant, estimated by linear regression of the terminal log-linear segment of the plasma log-concentration curve, and  $C_t$  is the last quantifiable concentration data point. In order to determine  $\lambda z$  by log-linear regression, at least 3 points will be used. The quality of log-linear regression and the reliability of extrapolated PK parameters should be demonstrated by an adjusted coefficient of determination  $R^2$  of at least 0.85;

- $C_{max}$  and  $t_{max}$ : the value and time of the maximum concentration will be obtained directly from the experimental data without interpolation;
- $t_{1/2}$ : the terminal half-life, associated with negative slope ( $-\lambda z$ ), calculated as  $0.693/\lambda z$  from the individual drug concentrations versus time profiles.
- $Dose_{IV}$ : is the actual IV dose calculated as [weight of full syringe (g) minus syringe weight after dose (g)] multiplied by nominal concentration ( $\mu\text{g/g}$ )
- $F_{inh}$ : inhaled absolute bioavailability based on  $AUC_{(0-\infty)}$  for CHF6001 calculated as  $F_{inh} = (AUC_{0-\infty\_inh} \times Dose_{IV}) / (AUC_{0-\infty\_IV} \times Dose_{inh})$ . If  $AUC_{0-\infty}$  is not calculable  $AUC_{0-t}$  will be used.
- $R_{b/p}$ : whole blood to plasma ratio is determined on the [C]-CHF6001 whole blood and plasma concentration ( $C_b$  and  $C_p$ ) 20 min after the start of infusion, calculated as  $R_{b/p} = C_b / C_p$
- $R_{bt/pt}$ : whole blood to plasma ratio is determined on the total-[C] whole blood and plasma concentration ( $C_{bt}$  and  $C_{pt}$ ) 20 min after the start of infusion, calculated as  $R_{bt/pt} = C_{bt} / C_{pt}$
- $CL$ : the total body plasma clearance following IV administration, calculated only for [C]-CHF6001 as  $Dose_{IV} / AUC_{0-\infty}$
- $CL_{blood}$ : the total body blood clearance following IV administration, calculated only for [C]-CHF6001 as  $CL_{blood} = CL / R_{b/p}$
- $V_{dss}$ : Volume of distribution at steady-state will be calculated only for [C]-CHF6001 as  $Dose_{IV} \times AUMC_{0-\infty} / (AUC_{0-\infty})^2$

Clinical Study Code: CLI-06001AA1-02	Version No.: 1.0
EUDRACT No.: 2020-004201-31	Date: 19 October 2020

- $V_z$ : the volume of distribution during the terminal phase, calculated only for [C]-CHF6001 as  $Dose_{IV}/(AUC_{0-\infty} \times \lambda_z)$
- $Fr_{plasma}$ : fraction of the relevant metabolites in plasma calculated as  $100 \times AUC [^{14}C]\text{-metabolite}/AUC [^{14}C]\text{-total radioactivity}$

The following PK parameters will be calculated, whenever possible, for each subject based on the concentrations of urine [C]-CHF6001 and urine [C]-total radioactivity:

- $Ae_u$ : amount excreted in urine (expressed in weight) over sampling interval calculated as:  $Ae_u = C_{ur} \times V_{ur}$ , where  $C_{ur}$  is the concentration in urine and  $V_{ur}$  is the volume of urine
- Cumulative  $Ae_u$ : cumulative amount excreted in urine, calculated as the sum of the amount excreted in urine for each collection period
- $fe_u$ : percent of the dose excreted in urine over a sampling interval, where  $fe_u = 100 \times (Ae_u/Dose_{IV})$
- $Fe_u$ : cumulative percent of dose excreted in urine, calculated as the sum of the percent of dose excreted in urine for each collection period
- $CL_R$ : renal plasma clearance calculated only for [C]-CHF6001, if plasma  $AUC_{0-\infty}$  is calculable then  $CL_R = \text{Cumulative } Ae_u/AUC_{0-\infty}$ , if Plasma  $AUC_{0-\infty}$  is not calculable then  $CL_R = \text{Cumulative } Ae_u/AUC_{0-t}$ .
- $CL_{R\_blood}$ : renal blood clearance calculated only for [C]-CHF6001, where  $CL_{R\_blood} = CL_R/R_{b/p}$
- $Fr_{urine}$ : fraction of the relevant metabolites recovered in urine calculated as amount recovered ( $Ar_u$ )/ $Dose_{IV} \times 100$

The following PK parameters will be calculated, whenever possible, for each subject based on plasma [C]-CHF6001 and urine [C]-CHF6001 radioactivity:

- $E_{h\_blood}$ : hepatic extraction calculated from intravenous systemic and renal blood clearance ( $CL_{blood} = CL/R_{b/p}$ ) and  $CL_{R\_blood} = CL_R/R_{b/p}$ , respectively and human hepatic blood flow ( $Q_H$ ; assumed to be 87 l/h [20]);  $E_{h\_blood} = (CL_{blood} - CL_{R\_blood})/Q_H$

The following PK parameters will be calculated, whenever possible, for each subject based on the concentrations of feces [C]-CHF6001 and feces [C]-total radioactivity:

- $Ae_f$ : amount excreted in the feces over sampling interval as  $Ae_f = (\text{concentration in faecal collected sample} \times \text{collected sample weight})$  for each faecal collection interval
- Cumulative  $Ae_f$ : cumulative amount excreted in feces, calculated as the sum of the amount excreted in feces for each collection period
- $fe_f$ : percent of the dose excreted in feces over a sampling interval, where  $fe_f = 100 (Ae_f/dose_{IV})$
- $Fe_f$ : cumulative percent of dose excreted in feces, calculated as the sum of the percent of dose excreted in feces for each collection period
- $Fr_{feces}$ : fraction of the relevant metabolites recovered in feces calculated as amount recovered ( $Ar_f$ )/ $Dose_{IV} \times 100$

The following PK parameters will be calculated, whenever possible, for each subject based on the concentrations of urine and feces [C]-CHF6001 and urine and feces [C]-total radioactivity:

Clinical Study Code: CLI-06001AA1-02	Version No.: 1.0
EUDRACT No.: 2020-004201-31	Date: 19 October 2020

- Cumulative  $Ae_{u+f}$ : cumulative amount excreted in urine and feces, calculated as Cumulative  $Ae_u$  + Cumulative  $Ae_f$
- $Fe_{tot}$ : cumulative percent of dose excreted in urine and feces, calculated as  $Fe_u + Fe_f$
- $Fr_{urine+feces}$ : fraction of the relevant metabolites recovered in urine and feces calculated as  $Fr_{urine} + Fr_{feces}$
- $Fe_{met}$ : Metabolized fraction calculated as  $Fe_{met} = [cumulative Ae_{u+f} (^{14}C\text{-total}) - cumulative Ae_{u+f} (^{14}C\text{-CHF6001})] / cumulative Ae_{u+f} (^{14}C\text{-total})$

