**[C]-CHF6001 1,85µg/ml (50nCi/ml) solution for IV infusion**

- *Active ingredient:* [C]-CHF6001
- *Formulation vehicle:* ethanol and kolliphor®HS 15 in 0.9% w/v saline
- *Appearance:* clear and colourless solution in a glass vial

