#### **Intravenous dose**

The proposed intravenous dose of 18.5µg (given over a 15-minutes infusion) accounts for less than 0.6% of the concomitant cold inhaled dose (3200µg). The overall dose (3218.5µg) is therefore expected to be well within the highest dose tested in humans (4800µg by inhalation).

The radioactive dose will be approximately 500nCi. The radioactive burden is considered to pose negligible additional risk above the background cosmic radiation, so no dosimetry estimation is necessary.

Clinical Study Code: CLI-06001AA1-02	Version No.: 1.0
EUDRACT No.: 2020-004201-31	Date: 19 October 2020

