9.1 Pharmacokinetic Analysis

The concentration ratios of whole blood [^{14}C]-total and [^{14}C]-CHF6001 radioactivity to plasma [^{14}C]-total and [^{14}C]-CHF6001 radioactivity, individual and cumulative mass balance of [^{14}C]-total radioactivity (amount (Ae_u , cumulative Ae_u , Ae_f and cumulative Ae_u) and percentage of dose (fe_u , Fe_u , fe_f and Fe_f) recovered as [^{14}C]-total radioactivity in urine, feces and total excreta) will be calculated by radioanalysis laboratory (██████████).

In addition, metabolites in plasma accounting for $\geq 10\%$ of total radioactivity recovered in this matrix, structural characterization may be performed, where possible. For metabolites in urine and feces (total excreta) accounting for $\geq 10\%$ of total administered radioactivity, structural characterization may be performed, where possible.

If available, fraction of the relevant metabolites in plasma ($\text{Fr}_{\text{plasma}}$), fraction of the relevant metabolites recovered in urine and feces (Fr_{urine} , Fr_{feces} , $\text{Fr}_{\text{urine+feces}}$) will be reported in a separate report together with structural characterization performed by radioanalysis laboratory (██████████).

Urine and Feces [^{14}C]-CHF6001 and [^{14}C]-total radioactivity

Parameter	Units ^a	Definition
Ae_u	mg	amount excreted in urine (expressed in weight) over sampling interval
Cumulative Ae_u	mg	cumulative amount excreted in urine, calculated as the sum of the amount excreted in urine for each collection period
fe_u	%	percent of the dose excreted in urine over a sampling interval
Fe_u	%	cumulative percent of dose excreted in urine, calculated as the sum of the percent of dose excreted in urine for each collection period
Ae_f	mg	amount excreted in the feces over sampling interval
Cumulative Ae_f	mg	cumulative amount excreted in feces, calculated as the sum of the amount excreted in feces for each collection period
fe_f	%	percent of the dose excreted in feces over a sampling interval

Fe _f	%	cumulative percent of dose excreted in feces, calculated as the sum of the percent of dose excreted in feces for each collection period
CL _R	L/h	renal plasma clearance (urine [¹⁴ C]-CHF6001 only)
CL _{R_blood}	L/h	renal blood clearance where CL _{R_blood} = CL _R /R _{b/p} (urine [¹⁴ C]-CHF6001 only)

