Plasma [¹⁴C]-CHF6001 and [¹⁴C]-total radioactivity

Parameter	Units ^a	Definition
[¹⁴ C]- CHF6001 and [¹⁴ C]- Total	AUC _(0-t) _iv	h*xg/mL area under the concentration-time curve from 0 to the last quantifiable concentration (t _{last}) ^b
[¹⁴ C]- CHF6001 and [¹⁴ C]- Total	AUC _(0-∞) _iv	h*xg/mL area under the concentration-time curve extrapolated to infinity ^c
[¹⁴ C]- CHF6001 and [¹⁴ C]- Total	%AUC _{extrap}	% percentage of AUC due to extrapolation from the last quantifiable concentration to infinity
[¹⁴ C]- CHF6001 and [¹⁴ C]- Total	C _{max_iv}	xg/mL the value of the maximum observed concentration
[¹⁴ C]- CHF6001 and [¹⁴ C]- Total	t _{max_iv}	h the time of the maximum observed concentration
	t _{last_iv}	h the time of the last quantifiable concentration
[¹⁴ C]- CHF6001 and [¹⁴ C]-Total	t _{1/2_iv}	h terminal half-life
[¹⁴ C]- CHF6001	CL	L/h total body plasma clearance (plasma [¹⁴ C]-CHF6001)
[¹⁴ C]- CHF6001	V _z	L volume of distribution during the terminal phase (plasma [¹⁴ C]-CHF6001)
[¹⁴ C]- CHF6001	V _{dss}	L volume of distribution at steady state (plasma [¹⁴ C]-CHF6001)
Plasma concentration of [¹⁴ C]-CHF6001/Total Radioactivity Ratio	NA	ratio of plasma concentration of [¹⁴ C]-CHF6001 to plasma concentration of [¹⁴ C]-total
AUC _(0-∞) Plasma [¹⁴ C]-CHF6001/Total Radioactivity Ratio	NA	AUC _(0-∞) of plasma [¹⁴ C]-CHF6001 relative to AUC _(0-∞) of plasma [¹⁴ C]-total radioactivity
C _{max} Plasma [¹⁴ C]-CHF6001/Total Radioactivity Ratio	NA	C _{max_iv} of plasma [¹⁴ C]-CHF6001 relative to C _{max_iv} of plasma [¹⁴ C]-total radioactivity

^a Units are based on concentration units (provided by the bioanalytical lab or preferred units for presentation of PK parameters) and dose units used in the study. For total radioactivity, C_{max} and AUC units will be presented as mass equivalents (ng Eq/g and h*ng Eq/g, respectively).

^b Area under the concentration-time curve will be calculated using the linear trapezoidal rule with linear interpolation

^c Based on the last observed quantifiable concentration

Blood [¹⁴C]-CHF6001 and [¹⁴C]-total radioactivity

Parameter	Units	Definition
[¹⁴ C]-CHF6001	R _{b/p}	NA whole blood to plasma ratio is to be determined on the [¹⁴ C]-CHF6001 whole blood and plasma concentration (C _b and C _p) 20 minutes after the start of infusion, calculated as R _{b/p} = C _b /C _p

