[¹⁴ C]-total	R _{bt/pt}	NA whole blood to plasma ratio is to be determined on the total-[¹⁴ C] whole blood and plasma concentration (C _{bt} and C _{pt}) 20 minutes after the start of infusion, calculated as R _{bt/pt} = C _{bt} /C _{pt}

Additional PK parameters may be determined where appropriate.

Concentration ratios of plasma [¹⁴C]-CHF6001 to plasma [¹⁴C]-total radioactivity will be listed by time point and summarized.

Pharmacokinetic analysis will be carried out using actual dose administered (mg) and actual blood sampling times post-dose. If an actual time is missing, the sample concentration result will be treated as missing unless there is scientific justification to include the result using the nominal time.

The parameters C_{max_inh}, C_{max_iv}, t_{last_inh}, t_{last_iv}, t_{max_inh} and t_{max_iv} will be obtained directly from the concentration-time profiles. If C_{max} occurs at more than 1 timepoint, t_{max} will be assigned to the first occurrence of C_{max}.

Inhaled absolute bioavailability (F_{inh}) based on AUC_(0-∞) will be calculated as follows:

$$F_{inh} = (AUC_{(0-∞)_inh} \times Dose_{iv}) / (AUC_{(0-∞)_iv} \times Dose_{inh}).$$

The parameter AUC_(0-t) or other common partial area may be used to determine F_{inh}, metabolite and total radioactivity ratios if AUC_(0-∞) cannot be reliably calculated for the majority of subjects.

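### Dose_IV is labelled actual but uses nominal strength; define it from the batch's measured radioactivity, with one stated specific activity for dose and samples

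*Protocol*

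**What the plan says.** Protocol section 8 states that Dose_IV "is the actual IV dose calculated as [weight of full syringe (g) minus syringe weight after dose (g)] multiplied by nominal concentration", in µg/g. The same section puts Dose_IV into F_inh, CL (and so CL_blood), Vdss and Vz. It is also the denominator of recovery, for both [14C]-CHF6001 and total 14C: fe_u is the "percent of the dose excreted in urine over a sampling interval, where" fe_u = 100 × Ae_u/Dose_IV, and fe_f is the "percent of the dose excreted in feces over a sampling interval, where" fe_f = 100 × Ae_f/Dose_IV.

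The product entry in Protocol section 6.1 gives the strength as "1,85µg/ml (50nCi/ml) solution for IV infusion", that is, per mL and not per gram.

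SAP 9.1 says: "Pharmacokinetic analysis will be carried out using actual dose administered (mg) and actual blood sampling times post-dose". SAP 9.1, 9.4 and 9.5 use the IV dose in their formulas, but none defines it. SAP section 12 declares no departure from the protocol.

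For total radioactivity, a footnote in SAP 9.1 says of C_max and AUC: "AUC units will be presented as mass equivalents (ng Eq/g and h*ng Eq/g, respectively". That requires a specific activity, and neither document names one. SAP 9.1 also gives total-14C recovery to the radioanalysis laboratory, while CL, Vz, Vdss and F_inh come from the non-compartmental PK analysis. It does not say that both use one Dose_IV.

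**The concern.** Weighing each syringe corrects the dose for how much solution a subject received. It cannot correct for how strong the solution was. That second factor is common to everyone dosed from the same batch, and the formula fixes it at nominal.

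Absolute bioavailability and mass balance are the study's main objectives, and both contain Dose_IV. F_inh sets an AUC of unlabelled drug against an AUC of 14C drug, so an error in 14C strength has nothing to cancel against. A shared factor moves mean and SD together, leaves the CV unchanged and does not shrink with more subjects. A low recovery could then be read as incomplete collection.

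**Working it through.** **Inputs.** From the documents: 10 mL infused (Protocol outline, study plan); 1.85 µg/mL and 50 nCi/mL (Protocol 6.1); the formulas of Protocol section 8. Assumed, because no value is given: rA = true/nominal radioactivity strength and rM = true/nominal mass strength, each 0.90 to 1.10.

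**1. The plan's own figures.** 10 × 1.85 = 18.5 µg; 10 × 50 = 500 nCi; 500 × 0.037 = 18.5 kBq; 18.5/3200 = 0.578%, under the stated 0.6%. All reproduce. Nominal specific activity = 50/1.85 = 27.03 nCi/µg. True specific activity = 27.03 × rA/rM.

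**2. General rule.** Reported/true CL = (dose used × specific activity used)/(true activity given). F_inh, CL_blood and Vz follow CL. Vdss does too, since Dose × AUMC/AUC² carries rA/rA² = 1/rA. Recovery takes the inverse factor.

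**3. Protocol dose, samples converted at nominal specific activity.** The factor is 1/rA, and a mass-only gap (rA = 1) gives 1.000.

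| rA | F_inh, CL, CL_blood, Vz, Vdss | Recovery | An assumed true 95% reads |
|---|---|---|---|
| 0.90 | 1/0.90 = 1.111 (+11.1%) | 0.90 | 85.5% |
| 0.95 | 1/0.95 = 1.053 (+5.3%) | 0.95 | 90.25% |
| 1.05 | 1/1.05 = 0.952 (-4.8%) | 1.05 | 99.75% |
| 1.10 | 1/1.10 = 0.909 (-9.1%) | 1.10 | 104.5% |

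A numerical non-compartmental analysis on the protocol's IV sampling times (assumed two-exponential profile, linear trapezoids, λz from the last five points) gave the same factors at all four values.

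E_h_blood moves by (1/rA - s)/(1 - s), where s is the renal share of blood clearance. For an assumed s of 0 to 0.10 this is 1.111 to 1.123 at rA 0.90, and 0.909 to 0.899 at rA 1.10.

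**4. What does not move.** CL_R and CL_R_blood (Ae and AUC both carry rA), Fe_met, Fr_plasma, the blood-to-plasma ratios and half-life.

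**5. Protocol dose, samples converted at a measured specific activity.** The factor is 1/rM for F_inh and CL, and rM for recovery. An rA-only gap now gives 1.000; rM of 0.90 or 1.10 gives 1.111 or 0.909.

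**6. Measured µg/g dose, nominal specific activity on samples.** The factor is rM/rA. With rA 0.90 and rM 1.10, CL is multiplied by 1.10/0.90 = 1.222 and recovery by 0.818. This is the mix to avoid.

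**7. Measured nCi/g dose, one specific activity throughout.** The factor is 1.000 for any rA and rM, whether that specific activity is nominal or measured.

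**8. Values reported in mass units.** AUC_iv, C_max_iv and Ae are not divided by dose. At nominal specific activity they carry rA/rM: 0.90/1.10 = 0.818 to 1.10/0.90 = 1.222 at the assumed extremes, and 1 if the two gaps are equal. Step 7 with nominal specific activity does not repair these.

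**9. Units.** The formula needs µg/g and no density is given. An assumed 0.98 to 1.02 g/mL turns 1.85 µg/mL into 1.888 to 1.814 µg/g, about ±2%.

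**The case against.** The shift needs two things that the documents do not establish: a gap in strength, and a particular conversion of samples. Protocol section 6 has the IV product certified by a QP and the radiolabelling methods validated, which bears on how likely a large gap is. The pharmacy and analytical protocols are not available here and may hold measured values. Because the label is per mL, the nominal µg/g figure may itself come from preparation data. The study is exploratory, with no test, no confidence interval and no criterion attached to F_inh, CL or recovery. All of this stands, and it means that the size is unknown. It does not change the formula, which calls for a nominal strength, or the SAP, which supplies no other.

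Three stronger readings are tempting and are not supported.

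- A reader might infer that the dose is in fact off target, from "The radioactive dose will be approximately 500nCi". That sentence belongs to the dose-selection and radiation-burden rationale. Other places give 500 nCi without the qualifier, and variation in delivered amount, which weighing captures, would explain the word.
- A reader might infer that a decision on metabolites hangs on Dose_IV, because excreta metabolites are considered at 10% or more "of total administered radioactivity, structural characterization may be performed, where possible". The step is optional, and the documents do not tie that threshold to a Dose_IV-based fraction.
- A reader might infer that every IV parameter is affected, or that specific activity always cancels. Steps 4 and 8 of the working show that neither is so.

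**Conclusion.** The point holds as a cheap improvement to a central quantity, not as a demonstrated error. The quantity labelled actual is half measured, and the plan as written would neither detect nor correct a strength gap.

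The +11.1% to -9.1% range for F_inh, CL, CL_blood, Vz and Vdss, and the ±10% for recovery, rest on an assumed rA of 0.90 to 1.10 and on conversion at nominal specific activity. If conversion uses a measured specific activity, the same range applies to rM. If the relevant strength is on target, these dose-based quantities do not shift.

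**What to change.** In SAP 9.1:

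- Define Dose_IV as delivered weight × measured radioactivity concentration (nCi/g) of the administered batch, converted to µg with the same specific activity that converts all plasma, blood, urine and feces 14C results.
- State that specific activity. Use the measured batch value where available, so that AUC_iv, C_max_iv and Ae in mass units are also right. With the nominal 27.03 nCi/µg, only the dose-normalised parameters and percent of dose are corrected.
- Require the same Dose_IV for parent and total 14C, at the PK group and at the radioanalysis laboratory.
- Rule out combining a measured µg/g dose with nominal specific activity on samples.
- If nominal strength is kept as a fallback, state the density used to go from µg/mL to µg/g.

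Record the change in SAP section 12.

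Cost: two short edits and one batch result passed to the analysts. If no result exists, one count per batch is needed, and the documents mention no retained aliquot. The assay's own error enters Dose_IV: an assumed 2% error moves F_inh, CL and recovery by about 2%, so the change helps only where that error is smaller than the gap it removes. F_inh would still rest on the nominal inhaled dose of 4 × 800 = 3200 µg.
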